11.1.1.2 Serious Adverse Event

An SAE is defined as any untoward medical occurrence that:

- Results in death
- Is life-threatening
- Requires inpatient hospitalisation or prolongation of existing hospitalisation
- Results in persistent or significant disability/incapacity
- Is a congenital anomaly/birth defect
- Results in vision loss or is vision threatening
- Is another important medical event(s)

The term 'life-threatening' in the definition of 'serious' refers to an event in which the subject is at risk of death at the time of the event. It does not refer to an event that hypothetically might cause death if it were more severe.

Hospitalisation that was pre-scheduled prior to obtaining the consent to participate in the study or for an elective procedure or routinely scheduled treatment for a pre-existing condition which has not worsened, does not constitute an SAE.

A prescheduled or elective procedure or a routinely scheduled treatment will not be considered an SAE, even if the subject is hospitalized. The study site must document all of the following:

- The prescheduled or elective procedure or routinely scheduled treatment was scheduled (or was on a waiting list to be scheduled) prior to obtaining the subject's consent to participate in the study.
- The condition requiring the prescheduled or elective procedure or routinely scheduled treatment was present before and did not worsen or progress in the opinion of the Investigator between the subject's consent to participate in the study and the time of the procedure or treatment.

- The prescheduled or elective procedure or routinely scheduled treatment is the sole reason for the intervention or hospital admission.

If a subject is hospitalized due to local requirements for administration of the study treatment, the hospitalization should not be considered an SAE unless one of the requirements in [Section 11.1.1.2](#) is met.

Other events that may not result in death, are not life-threatening or do not require hospitalisation, may be considered an SAE when, based upon appropriate medical judgment, the event may jeopardise the subject and may require medical or surgical intervention to prevent 1 of the outcomes listed above.

Vision Loss to be Reported as Serious Adverse Events

Vision Loss not to be Reported as an SAE:

- Surgery-related BCVA decrease of ≥ 15 letters on ETDRS chart occurring within 1 day of surgery, but recovering / resolving at post-operative Days 7 and 14.

Vision Loss or Vision-Threatening Event to be Reported as an SAE:

- Surgery-related BCVA decrease of ≥ 15 letters on ETDRS chart that occurs within 1 day of surgery and that has not recovered* by the 1-Month Visit.
- A decrease in BCVA of ≥ 15 letters on ETDRS chart that occurs within 1 day of surgery, however, in the Investigator's opinion:
 - Has an evolution not consistent with the expected post-operative course;
 - May be attributable to a complication that occurred during surgery, or another untoward event, or the study drug;
 - Actually or potentially requires any surgical or medical intervention to prevent permanent loss of vision.
- Non-surgery-related, sustained (>48 hours duration) decrease from baseline in BCVA of ≥ 15 letters on ETDRS chart.

*Recovery / Resolution of BCVA is defined as a return to baseline BCVA within 5 letters on the ETDRS chart.

11.1.2 Recording of Adverse Events

AEs/SAEs will be collected from the time the subject provides written informed consent (Screening Visit) through Period 2, Visit 9 (Month 12 ± 14 Days or ET Visit, if applicable).

Subjects will be questioned on the occurrence of an AE at every visit including any unscheduled visit, by using non-leading questioning such as 'How have you been since the last visit?'

All AEs occurring during the study observed by the Investigator or reported by the subject, whether or not attributed to study drug or the surgical procedure, will be recorded in the subject's medical records and in the eCRF. Any clinically significant changes in laboratory results or vital sign measurements (as determined by the Investigator) are to be recorded as an AE.

Ocular AEs are to be recorded on a per-eye basis.

The following information will be recorded in the eCRF for each AE: description, date of onset and end date, outcome, severity, assessment of relatedness to study drug/study procedure, the action taken and confirmation of whether the event is considered serious (see [Section 11.1.1.2](#) for the definition of seriousness). Follow-up information should be provided as necessary (see [Section 11.1.3](#) for specifics on follow-up procedures).

AE severity and relationship to the study drug or the surgical procedure will be assessed at the site by the Investigator or a medically qualified designee.

AE Severity

The severity of events will be assessed on the following scale:

- 1 = mild (awareness of sign or symptom, but easily tolerated)
- 2 = moderate (discomfort sufficient to cause interference with normal activities)
- 3 = severe (incapacitating, with inability to perform normal activities).

AE Relationship

When assigning relatedness of the AE, consideration will be given to whether there is a plausible relationship to either the study drug or the surgical procedure. The following are definitions of relatedness that will be used in this study:

Unrelated: The event is not reasonably related in time to the administration of the study drug/surgical procedure, or exposure of the study drug/surgical procedure has not yet occurred, or biologic plausibility does not exist

Related: A reasonable possibility exists that the study drug / study procedure caused the AE. A suspected AE can be further defined by:

Possibly related: a relationship is clinically or biologically reasonable relative to the administration of the study drug/surgical procedure, but the event could have been due to another equally likely cause

Probably related: a relationship is clinically/biologically reasonable relative to the administration of the study drug/surgical procedure, and the event is more likely explained by exposure to/administration of the study drug/surgical procedure than by other factors and causes

Definitely related: there is a causal relationship of the onset of the event, relative to administration of the study drug/surgical procedure and there is no other cause to explain the event.

When a relationship is determined to exist, the Investigator or medical designee will further define if that relationship is to the *study drug*, the *study procedure*, *both*, or *unknown*.

11.1.3 Follow-up of Adverse Events

AEs will be followed until the subject has recovered or the subject's participation in the study is complete.

Subjects who are withdrawn from the study as a result of a drug-related AE will be followed up until the event has resolved, subsided, stabilised, or the subject withdraws consent or is lost to follow-up.

All SAEs, regardless of attribution to study drug or the surgical procedure, should be followed-up until the event has resolved, subsided, stabilised, or the subject withdraws consent or is lost to follow-up. The Sponsor (or designee) will follow up on SAE reports to completion. Investigators are expected to provide the requested additional information for a complete assessment and documentation of the SAE reports in a timely manner.

11.1.4 Reporting of Serious Adverse Events

The Investigator shall immediately (within 24 hours of learning of the event) report any SAE to the Sponsor (or its designee) by completing and emailing the SAE form. For reporting purposes, the date of SAE form submission by the Investigator to the Sponsor will be designated as Day 0.. The initial report shall be promptly followed up with a more detailed report providing specifics about the subject and the event. Copies of hospital reports, autopsy reports, and other documents should be provided (if applicable).

The Sponsor will report SAEs and SUSARs to investigative sites, the Institutional Review Board (IRB)/Independent Ethics Committee (IEC), and regulatory authorities in compliance with current regulations. All cases that are fatal or life-threatening will be reported immediately after the Sponsor received the initial report from the Investigator. All non-fatal or non-life-threatening cases will be reported within a maximum of 15 days after the initial Investigator's report. The Sponsor will also provide periodic safety reports to IRBs/IECs and regulatory authorities, as applicable. Follow-up SAE reports will be submitted within 15 days of receiving the information.

A sample SAE form is provided in the Study Operations Manual, along with the SAE reporting contact information.

11.1.5 Data Monitoring Committee

An independent Data Monitoring Committee (DMC) will be used in this study to safeguard the safety and interests of study subjects and assess the safety and risk/benefit of the gene therapy intervention during the trial.

At regular intervals during the study, the DMC will review the progress and accrued study data and provide advice to the Sponsor on the efficacy and safety aspects of the study. The DMC will also inform the Sponsor if there is a consensus that the ongoing data show that the gene therapy, its method of administration, and/or the study design are no longer in the best interests of study subjects. Details of DMC organisation and responsibilities are included within a DMC charter.

11.2 Pregnancy

Any pregnancy that occurs during the clinical study in a female partner of a study subject should be recorded on a Pregnancy Notification Form. Consent from the pregnant partner is required prior to the collection of personal data. However, the Investigator shall immediately (within 24 hours of learning of the event) report the pregnancy, with at least preliminary data, to the Sponsor (or its designee) by completing and emailing the Pregnancy Notification Form. Follow-up information including delivery, termination, and any congenital abnormality should be reported within 24 hours of the study site staff becoming aware.

11.3 Stopping Criteria

- Severe ocular inflammation (e.g. endophthalmitis) that is unresponsive to treatment should result in the affected subject not being treated in the second eye. However, the subject will continue to be followed for safety for the duration of the study.
- At the request of the DMC, the trial may be stopped based on specific safety concerns (i.e., SUSARs), not defined in the Investigator's Brochure (Section 6.3).
- The study may be discontinued if the Sponsor deems it necessary for medical, safety, regulatory, business, or other reasons consistent with applicable laws or regulations.

11.4 Laboratory Assessments

11.4.1 Vector Shedding

Blood, tears (both eyes), urine and saliva samples will be collected at the times indicated in [Table 1](#) and tested using an appropriate assay for evidence of vector shedding and dispersion. Samples will be sent to a central laboratory for analysis. Refer to the Study Operations Manual for details on the shipping and handling of samples.

11.4.2 Immunogenicity

For the evaluation of immunogenicity, blood will be collected at the times indicated in [Table 1](#). Selected samples will be analysed.

Immunoassays are planned to assess cell-based and antibody-based immune responses against AAV2-REP1. Enzyme-linked immunospot (ELISPOT) assays will be used for the assessment of T-cell-mediated immune responses to transgene product (REP1) and the capsid. Antibody responses against the capsid and transgene product will be measured using a cell-based neutralization assay and an enzyme-linked immunosorbent assay (ELISA), respectively.

Refer to the Study Operations Manual for details on the shipping and handling of samples.

Remaining samples may be stored for up to 15 years or per local regulations.

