13 STATISTICAL CONSIDERATIONS

13.1 Sample Size

Approximately 60 subjects are planned to be enrolled in the study. A total of 120 treated eyes is considered sufficient to characterise the immunological profile of bilateral AAV2-REP1 administration, which is the key concern of gene therapy re-administration.

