16 APPENDIX

Table 1 presents a schedule of study procedures.

Table 1: Schedule of Study Procedures

Visit	Period 1 Screening ^a	Period 2 Baseline ^b (<10 Weeks from Visit 1, Period 2)	Study Period 1 / Period 2									ET Visit ^d	Unscheduled Visit ^e
			V1	V2	V3	V4	V5	V6	V7	V8	V9		
Study Day/Month Visit Window			Day 0 Injection Day ^c (≤10 weeks Screening)	Day 1 Post op	Day 3 +2 d	Day 7 - 1/+2 d	Day 14 ± 3d	M 1 ± 7d	M 3 ± 14d	M6 ± 14d	M 12 ± 14d		
Assessment/Procedures (All subjects/eyes)													
Informed Consent	X												
Demography, medical and ocular history	X												
Vital signs (pulse, blood pressure)	X	X		X	X						X	X	
Weight ^f	X	X											
Vector shedding sampling ^g	X	X		X	X	X	X	X			X ^h		
Immunogenicity sampling ⁱ	X	X		X		X	X	X	X	X	X	X	
BCVA	X	X		X	X	X	X	X	X	X	X	X	X
Microperimetry	X	X						X	X	X	X	X	
Full ophthalmic exam ^j	X	X	X	X	X	X	X	X	X	X	X	X	X
SD-OCT	X	X		X		X	X	X	X	X	X	X	X
Autofluorescence	X	X				X	X	X	X	X	X	X	
7-field colour fundus photos ^k	X	X									X	X	
Study drug / sub-retinal injection / vitrectomy / retinal detachment			X										
AE/SAE monitoring ^l	X	X	X	X	X	X	X	X	X	X	X	X	X

Visit	Period 1 Screening ^a	Period 2 Baseline ^b (<10 Weeks from Visit 1, Period 2)	Study Period 1 / Period 2									ET Visit ^d	Unscheduled Visit ^e
			V1	V2	V3	V4	V5	V6	V7	V8	V9		
Study Day/Month Visit Window			Day 0 Injection Day ^c (≤10 weeks Screening)	Day 1 Post op	Day 3 +2 d	Day 7 - 1/+2 d	Day 14 ± 3d	M 1 ± 7d	M 3 ± 14d	M6 ± 14d	M 12 ± 14d		
Assessment/Procedures (All subjects/eyes)													
Concomitant medication, procedures, and treatment review ^m	X	X	X	X	X	X	X	X	X	X	X	X	X

Abbreviations: AE=adverse event; BCVA=best corrected visual acuity; ET=early termination; IOP=intraocular pressure; LOCS=lens opacities classification system; SAE=serious adverse event; SD-OCT=spectral domain optical coherence tomography; SE1=Study Eye 1; SE2=Study Eye 2

^a Screening Visit/Period must be performed ≤10 weeks of Period 1, Visit 1. Selection of SE1 and SE2 will be determined by the Investigator in collaboration with the subject.

^b Baseline assessments must occur before the SE2 is dosed. These can occur at a regularly scheduled visit if that visit is within 10 weeks prior to surgery in SE2. If it has been more than 10 weeks since a visit, the subject must return for assessments at this Baseline Period 2 visit.

^c Subjects will undergo vitrectomy and AAV2-REP1 administration to SE1 in Period 1; SE2 in Period 2.

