^d ET visit is to be performed if a subject discontinues at any time.

^e If clinically indicated, subjects may need to return to the site for an unscheduled visit. At a minimum, the following assessments will be performed: BCVA, full ophthalmic examination, SD-OCT, AF, concomitant medication, procedures, and treatment review and AE/SAE monitoring.

^f Weight is collected for dose calculation of the corticosteroid regimen.

^g Blood, tears (both eyes), urine and saliva samples.

^h If ET visit occurs within 3 months post-treatment.

ⁱ Immunoassays are planned to assess cell-based and antibody-based immune responses against AAV2-REP1. Enzyme-linked immunospot (ELISPOT) assays will be used for the assessment of T-cell-mediated immune responses to transgene product (REP1) and the capsid. Antibody responses against the capsid and transgene product will be measured using a cell-based neutralization assay and an enzyme-linked immunosorbent assay (ELISA), respectively. All immunogenicity samples will be sent to a central laboratory for analysis.

^j The ophthalmic examination will include IOP, slit lamp examination, lens opacity grading, and dilated ophthalmoscopy. The same slit lamp machine and lighting conditions should be used across the study for each subject.

^k Stereo photos for fields 1, 2, 3.

^l AEs/SAEs will be collected from the time the subject provides written informed consent (Screening Visit) through Period 2, Visit 9 (or ET Visit, if applicable).

^m Subjects will be given a course of oral corticosteroid before each surgical visit, and instructed to start taking the drug 2 days prior to SE1/SE2 treatment, unless the SE2 surgical treatment coincides with the SE1 steroid treatment period, when an extended course of steroid can cover both surgical treatments. This regimen is outlined in detail in [Section 9.8](#).

For SE1, the Full Corticosteroid Regimen should be initiated as described. For SE2, and surgeries that occur on day 21 or later, the Full Corticosteroid Regimen should be initiated as described, beginning 2 days before the scheduled SE2 surgery. If SE2 is to be performed prior to Study Day 21, then the Full Corticosteroid Regimen should be initiated 2 days prior to the scheduled surgery for SE2, and this will supersede the steroid taper in progress for SE1. The full 21 days of treatment will then be completed for SE2.

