4.17.11.2 Assay Positivity by Visit

The number and percentage of subjects with positive results at each visit will be presented by baseline status (such as screen positive, negative etc) and by treatment group. The positivity analysis for ELISpot will be summarized for the overall treatment of BIIB111 as well as with respect to either REP1 or AAV2.

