4.17.11.4 Relationship Between Immunogenicity Assay and Safety

The relationship between the immunogenicity assays (ADA, Nab and ELISpot) and selected adverse events will be assessed. These adverse events include ocular inflammation-related adverse events, visual acuity reduced-related adverse events and hypersensitivity-related adverse events. The number and percentage of post-treatment (treatment-emergent) ocular inflammation-related adverse events, visual acuity reduced-related adverse events and hypersensitivity-related adverse events (based on the adverse event data), as well as the number and percentage of eyes with a decrease from baseline of ≥ 15 letters in BCVA at Month 12 (based on the visual acuity assessment data) will be summarized by (1) subjects with negative assay at period 1 baseline; and (2) subjects with positive assay at period 1 baseline; and (3) subjects with at least one treatment-emergent positive assay at any visit during the study; and (4) subjects with no treatment-emergent positive assay during the study. In (3) and (4), to determine the treatment-emergent positivity, the period 1 baseline will be used to calculate the change from baseline for data in period 1 and period 2 baseline will be used to calculate the change from baseline for data in period 2.

The analyses will be conducted by eye, by period and surgery window. It will be repeated by AE severity (mild, moderate and severe) and by AE time to onset (≤ 30 days and > 30 days post-surgery). If an AE has more than one occurrence with an onset ≤ 30 days and another > 30 days, the AE will be reported in both ≤ 30 days and > 30 days' time to onset categories.

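### Which immunogenicity samples are assayed is stated inconsistently and without a rule; if only some are, SAP 4.17.11.4 files sparsely tested subjects as having no treatment-emergent response

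*Protocol*

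**What the plan says.** Protocol 11.4.2 says "Selected samples will be analysed" and adds "Remaining samples may be stored for up to 15 years or per local regulations", so it foresees that some samples will stay untested. It does not say who selects, when, or on what basis. Its only pointer elsewhere is "Refer to the Study Operations Manual for details on the shipping and handling of samples", which does not cover selection.

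Other current text points the other way. Footnote i to Table 1 of the protocol says "All immunogenicity samples will be sent to a central laboratory for analysis", and footnote i to Table 3 of the SAP repeats it. SAP 4.17.11 describes ELISpot testing against four peptide pools at each visit. The SAP nowhere mentions sample selection.

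The planned outputs are:

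- SAP 4.17.11.2: "The number and percentage of subjects with positive results at each visit will be presented by baseline status".
- SAP 4.17.11.3: treatment-emergent status by visit, period and surgery window. A visit without a valid sample, or without a valid baseline, is missing and is excluded.
- SAP 4.17.11.4: selected adverse events, and BCVA loss of 15 letters or more at Month 12, tabulated for four groups. Group (3) is "subjects with at least one treatment-emergent positive assay at any visit during the study"; group (4) is subjects with none during the study.

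Under SAP 4.1, a baseline sample and one evaluable post-surgery sample are enough to enter the Immunogenicity analysis set.

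**The concern.** Group (3) needs one positive result and group (4) needs only the absence of one. The fewer samples a subject has tested, the more likely he is to land in group (4) whatever his true response. The missing-data rule that protects the by-visit tables is not carried into this split, and no minimum amount of testing is set.

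Two things would be at stake. Partial testing unrelated to outcome would undercount responders and pull the two groups' event rates together. Testing that followed clinical events would separate the groups with no biological cause, and in an unmasked study no text in either document rules that out. Protocol 13.1 rests the sample size on the immunological profile of bilateral administration, "which is the key concern of gene therapy re-administration", so these tables carry more weight here than in most descriptive studies.

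**Working it through.** The plan gives no figure to reproduce: there is no formal sample size calculation, and neither document states a response rate, its persistence, or the number of samples to be assayed. The only design arithmetic, 60 subjects × 2 eyes = 120, does not bear on the point.

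**Input from the documents.** The "Immunogenicity sampling" row of Table 1 schedules Visits 2, 4, 5, 6, 7, 8 and 9 after each surgery, which is 7 post-surgery samples in a complete period.

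**Assumed inputs.** k = visits at which a true responder would test positive (1 to 3); m = samples assayed out of 7, chosen at random; response rate 20%; event rate 20%.

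**Step 1. Chance that a true responder shows no positive in one complete period.**

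P(miss) = C(7−k, m) / C(7, m)

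| k | m = 2 | m = 3 | m = 5 | m = 7 |
|---|---|---|---|---|
| 1 | 15/21 = 71% | 20/35 = 57% | 29% | 0% |
| 2 | 10/21 = 48% | 10/35 = 29% | 5% | 0% |
| 3 | 6/21 = 29% | 4/35 = 11% | 0% | 0% |

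**Step 2. Effect on the groups.** Of 60 subjects, 0.20 × 60 = 12 respond. Full testing gives 12 in group (3) and 48 in group (4). With m = 2 to 3 and k = 1 to 3:

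- Most misfiling (k = 1, m = 2): 12 × 0.714 = 8.6 misfiled, leaving 3.4 in group (3) and 56.6 in group (4).
- Least misfiling (k = 3, m = 3): 12 × 0.114 = 1.4 misfiled, leaving 10.6 and 49.4.

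Misfiled responders would make up between 1.4/49.4 = 3% and 8.6/56.6 = 15% of group (4). Testing unrelated to outcome therefore mainly shrinks group (3) and weakens a real difference. It does not create one.

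**Step 3. Effect if testing followed events.** Suppose events and response are independent, every sample is assayed in subjects with an event, and half are assayed in the others. A response visible at one visit is then found with probability 1 and 0.5 respectively.

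- Group (3) share: 0.20 × (0.20 × 1 + 0.80 × 0.5) = 0.12. Of this, 0.20 × 0.20 = 0.04 has an event, so the event rate is 0.04/0.12 = 33%.
- Group (4) share: 1 − 0.12 = 0.88. Of this, 0.20 − 0.04 = 0.16 has an event, so the event rate is 0.16/0.88 = 18%.

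The ratio is about 1.8 with no true link. If the others have 2 to 3 of 7 samples assayed and k runs from 1 to 3, the range is 22-47% in group (3) against 17.5-19.6% in group (4).

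**The case against.** The strongest reply is that selective testing is not established. Two footnotes and the ELISpot description favour full testing against one sentence in 11.4.2, so this may be a drafting conflict. That stands, and every figure above is conditional on it. It does not dispose of the point. The change log for protocol version 3.0 records the 11.4.2 wording as a deliberate change, and sending all samples to a laboratory is compatible with assaying only some.

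The SAP also has safeguards. Subjects with no evaluable post-surgery sample are outside the analysis set (4.1), missing-data patterns will be examined (4.8), and individual results will be listed beside events of interest (4.17.11.5). These would let a careful reader see thin testing, but none changes who enters group (4).

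A reader might infer three stronger things that the documents do not support:

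- That untested visits count as negative throughout. SAP 4.17.11.3 excludes them from the by-visit treatment-emergent tables; what remains there is a selected denominator. SAP 4.17.11.2 does not state the denominator for by-visit positivity.
- That samples were, or will be, chosen according to adverse events. The text permits this and nothing suggests it. A rule may exist in a document not supplied, although none is cited for the purpose.
- That the step 3 assumptions give a table reading 20% against 10%. Those are positivity rates by event status. SAP 4.17.11.4 tabulates events by assay group, so the relevant contrast is 33% against 18%.

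Finally, the study makes no formal comparisons, so no error rate is affected.

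**Conclusion.** The point holds in a limited form. The current texts conflict on which samples are assayed, no selection rule is given, and group (4) has no minimum testing requirement. If testing is selective, 57-71% of responders positive at one visit, or 11-29% of those positive at three, would be misfiled with 2 to 3 of 7 samples assayed. The chance falls to zero with full testing. These figures cover one complete period with random selection and rest on assumed persistence and testing intensity. The false association of about 33% against 18% needs the further assumption of event-driven testing, which is a possibility and not a finding. Severity is moderate: the analysis is descriptive, but it serves the stated reason for the sample size.

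**What to change.** 1. **Protocol 11.4.2, footnote i of both schedules, and SAP 4.17.11.** Make them agree. State that each assay is run on all scheduled samples, or on one fixed set of visits relative to each surgery, identical for all subjects and chosen without reference to adverse events or earlier results.

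2. **SAP 4.17.11.4.** Admit a subject to group (4) only with a valid baseline and valid results at the fixed-set visits due for him. Show other subjects without a positive as *not determined*. The words *due for him* are needed because Period 1 stops at second-eye surgery. Short-window subjects generally do not reach its Month 6 or Month 12 visit, and medium-window subjects generally do not reach Month 12. Requiring every Table 1 visit could bar about 20 + 20 = 40 of 60 subjects from group (4) while leaving group (3) open to them. State also which visits count for the 6 subjects first treated in an antecedent study: SAP 4.3 makes an immunogenicity exception for them, while SAP 4.4 keeps antecedent data out of the report.

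3. **Reporting.** Tabulate samples collected and samples analysed by visit and assay, and state the denominator in SAP 4.17.11.2.

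The cost is a few sentences of text, some extra tabulation and a probably small *not determined* group. The blood is already drawn under the schedule. Assay cost rises only if full testing is chosen and was not already intended; a fixed subset can be sized to what is affordable. The rule should be written before results and events are examined together.
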